8.6. Safety and Tolerability Assessments

8.6.1. Adverse Events

All AEs will be coded using the Medical Dictionary for Regulatory Activities (MedDRA) Version 22.1. All AEs will be assigned severity grade using National Cancer Institute Common Terminology Criteria for Adverse Events (CTCAE) Version 5.0.

A treatment-emergent adverse event (TEAE) will be defined as an AE that starts during or after the first dose, or starts prior to the first dose and increases in severity after the first dose.

A treatment-related TEAE will be defined as a TEAE with a relationship of related to the study treatment (LOXO-305 or itraconazole or rifampin), as determined by the investigator.

For Part 1 of this study, the assignment of TEAEs to the associated treatments will be as follows:

- A TEAE occurring during or after Day 1 dosing and prior to Day 8 dosing will be assigned to 200 mg LOXO-305
- A TEAE occurring during or after Day 8 dosing and prior to Day 12 dosing will be assigned to 200 mg itraconazole
- A TEAE occurring during or after Day 12 dosing will be assigned to 200 mg LOXO-305 and/or 200 mg itraconazole

For Part 2 of this study, the assignment of TEAEs to the associated treatments will be as follows:

- A TEAE occurring during or after Day 1 dosing and prior to Day 8 dosing will be assigned to 200 mg LOXO-305
- A TEAE occurring during or after Day 8 dosing will be assigned to 200 mg LOXO-305 and/or 600 mg rifampin

All AEs will be listed. In addition to the data recorded in the database, the listings will include derived onset time and duration. Onset time will be calculated from the time of the last dose for TEAEs only.

The frequency of subjects with TEAEs and the number of TEAEs will be summarized for the following categories:

- TEAEs (overall, serious, and leading to discontinuation) by treatment
- TEAEs by severity and treatment

- Treatment-related TEAEs (overall, serious, and leading to discontinuation) by treatment
- Treatment-related TEAEs by severity and treatment

The frequency of subjects will be summarized separately for TEAEs and treatment-related TEAEs by the following:

- System organ class, preferred term, and treatment
- Preferred term and treatment
- System organ class, preferred term, day of onset, and treatment

For the AE data the following rules will apply:

- For the derivation of TEAE status: If the start date/time of an AE is incomplete or missing, an AE will be assumed to be a TEAE, unless the incomplete start date/time or the end date/time indicates an AE started prior to the first dose.
- For the derivation of treatment-related TEAE status: If the study treatment relationship for a TEAE is missing, a TEAE will be assumed to be a treatment-related TEAE.
- For the derivation of onset time: If the start date/time of an AE is missing, onset time will not be calculated. If the start date/time of an AE is incomplete, where possible, the minimum possible onset time will be calculated and presented in '≥DD:HH:MM' format (eg, if the date/time of the last dose is 01MAY2019/08:00 and recorded start date/time of an AE is 03MAY2019, then the minimum possible onset time will be calculated by assuming the AE started at the first hour and minute of 03MAY2019 [03MAY2019/00:00], thus will be presented as onset time ≥01:16:00 in the listing).
- For the derivation of duration: If the end date/time of an AE is missing, duration will not be calculated. If the start or end date/time of an AE is incomplete, where possible, the maximum possible duration will be calculated and presented in '≤DD:HH:MM' format (eg, if the start of an AE date/time is 01MAY2019/08:00 and its recorded end date/time is 03MAY2019, then the maximum possible duration will be calculated by assuming the AE ended at the last hour and minute of 03MAY2019
 [03MAY2019/23:59], thus will be presented as duration ≤02:15:59 in the listing).
- For the calculation of summary statistics: If the severity of a TEAE is missing, a TEAE will be counted under the maximum severity possible, up to Grade 4 in the absence of a fatal outcome.
- For the calculation of summary statistics: If a subject experienced multiple TEAEs with the same preferred term for the same treatment, this will be counted as 1 TEAE for that treatment under the maximum severity recorded.

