11. APPENDICES

Appendix 1: Adverse Event Reporting

Adverse Events

Definition of Adverse Events

An adverse event (AE; or adverse experience) is defined as any untoward medical occurrence experienced by a patient or healthy adult subject, whether or not considered drug-related by the Investigator (or designee). A treatment-emergent adverse event (TEAE) is an AE that is reported after a dose of study drug.

The following are all AEs:

- unfavorable changes in general condition;
- subjective or objective signs/symptoms;
- concomitant diseases or accidents;
- clinically relevant adverse changes in laboratory parameters observed in a subject during a clinical study.

Adverse events comprise all disturbances of general health status, subjective and objective disease symptoms (including laboratory abnormalities that are deemed clinically significant by the Investigator or designee), and accidents observed in the context of a clinical trial, irrespective of a possible causal relationship with the administration of the trial substance.

Categorization of Adverse Events

The severity of AEs will be categorized based on the National Cancer Institute Common Terminology Criteria for Adverse Events (CTCAE) Version 5.0 as follows:

- **Grade 1 Mild:** Asymptomatic or mild symptoms; clinical or diagnostic observations only; intervention not indicated
- **Grade 2 Moderate:** Minimal, local or noninvasive intervention indicated; limiting age-appropriate instrumental Activities of Daily Living (ADL)*
- Grade 3 Severe or medically significant but not immediately life-threatening: Hospitalization or prolongation of hospitalization indicated; disabling; limiting self-care ADL**
- Grade 4 Life-threatening consequences: An event that puts the patient at immediate risk of death
- **Grade 5** Death related to AE.

Note: Not all grades are appropriate for all AEs. Therefore, some AEs are listed within the CTCAE with fewer than 5 options for grade selection. Grade 5 (death) is not appropriate for some AEs and therefore is not an option. * Instrumental ADL refer to preparing meals, shopping for groceries or clothes, using the telephone, managing money, etc. **Self-care ADL refer to bathing, dressing and undressing, feeding self, using the toilet, taking medications, and not bedridden. The Investigator (or designee) will make a determination of the relationship of the AE to the study drug using a 2-category system according to the following guidelines:

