2.2. Secondary Objectives

The secondary objectives of this study are:

• To assess the safety and tolerability of a single oral dose of LOXO-305 when administered alone and co-administered with multiple oral doses of itraconazole.

• To assess the safety and tolerability of a single oral dose of LOXO-305 when administered alone and co-administered with single and multiple oral doses of rifampin.

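### SAP 8.6.1 has no rule for an AE that begins under one treatment and worsens after the next starts, so worsening on the combination can be tabulated under LOXO-305 alone

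*SAP*

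**What the plan says.** SAP Section 8.6.1 gives two routes to treatment-emergence: the AE begins at or after the first dose, or it "starts prior to the first dose and increases in severity after the first dose". The missing-date rule uses the same single anchor: an AE with an incomplete date is taken as emergent "unless the incomplete start date/time or the end date/time indicates an AE started prior to the first dose". The protocol definition (Appendix 1) is looser. A TEAE there "is an AE that is reported after a dose of study drug", with no mention of worsening.

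TEAEs are then assigned to treatments by window. In both parts the first window is "A TEAE occurring during or after Day 1 dosing and prior to Day 8 dosing will be assigned to 200 mg LOXO-305". Part 1 continues with "A TEAE occurring during or after Day 8 dosing and prior to Day 12 dosing will be assigned to 200 mg itraconazole" and "A TEAE occurring during or after Day 12 dosing will be assigned to 200 mg LOXO-305 and/or 200 mg itraconazole". Part 2 has one further window: "A TEAE occurring during or after Day 8 dosing will be assigned to 200 mg LOXO-305 and/or 600 mg rifampin".

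The section plans subject counts by severity and treatment, and separately by system organ class, preferred term and treatment. Its maximum-severity rule covers repeated TEAEs of one preferred term within one treatment. It does not cover one AE that spans two treatments. Neither document says whether *occurring* means onset, or whether a change in grade opens a new AE record.

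**The concern.** The secondary objectives (SAP Section 2.2) ask about safety when LOXO-305 is "administered alone and co-administered with multiple oral doses of itraconazole", and likewise with rifampin. The by-treatment AE tables are among the main summaries that bear on this. The treatments are separated in time by dosing days, yet the only boundary at which the SAP recognizes worsening is the first dose.

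An AE that starts mildly on LOXO-305 alone and becomes severe after co-administration is what an interaction study would want to see in the co-administration column. The protocol treats this as plausible: Section 3.3 anticipates higher exposure, and Section 1.6 adds a sentinel group to Part 1 because LOXO-305 has not been given with a CYP3A4 inhibitor in healthy adults before. If such an AE is kept under the treatment on which it began, the error has one direction. The co-dose always follows LOXO-305 alone, so worsening can be credited only to an earlier treatment.

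**Working it through.** No figure in the plan depends on this point, so there is nothing to reproduce. The check applies the SAP's own windows to hypothetical AEs.

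**Inputs**
- Part 1 windows (SAP 8.6.1): Day 1 to before Day 8, LOXO-305 alone; Day 8 to before Day 12, itraconazole alone; Day 12 onward, combination.
- Part 2 windows (SAP 8.6.1): Day 1 to before Day 8, LOXO-305 alone; Day 8 onward, combination.
- 12 subjects in each part (SAP Section 5), all assumed to be in both columns' denominators.
- Assumed AE: Grade 1 from Day 5, ongoing, Grade 3 on the day after the co-dose (Day 13 in Part 1, Day 9 in Part 2). The documents give no frequency for such events.

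**Step 1: where the AE lands.** The result is the same in both parts.

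| Reading of the SAP | LOXO-305 alone | Co-administration |
|---|---|---|
| A. One record at maximum grade, placed by onset | Grade 3 | no event |
| B. One record at maximum grade, placed in every window where it is ongoing | Grade 3 | Grade 3 |
| C. New record at each grade increase, placed by onset | Grade 1 | Grade 3 |

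In Part 1, an AE that starts on Day 9 and worsens on Day 13 behaves the same way. Reading A gives Grade 3 under itraconazole alone and nothing under the combination; reading C gives Grade 1 and Grade 3.

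Only reading C puts each grade under the treatment on which it was reached. Reading A loses the event from the combination column, and reading B overstates LOXO-305 alone.

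**Step 2: which reading the text favors.** If every grade increase opened a new record, a worsening after the first dose would be a new AE starting after that dose. It would already qualify as a TEAE, and the worsening clause would have no work to do. Section 8.6.1 also derives duration from one start and one end per AE, and plans a table by day of onset and treatment. These features point to reading A but do not state it.

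**Step 3: size for one affected subject.**
- One subject in a column: 1/12 = 8.3 percentage points.
- Preferred-term table. Reading A: 1/12 alone, 0/12 combination. Worsening placed correctly: 1/12 and 1/12. One column changes, and the difference moves by 1/12 = 8.3 points.
- Grade 3 row of the severity table. Reading A: 1/12 alone, 0/12 combination, a difference (combination minus alone) of −8.3. Placed correctly: 0/12 and 1/12, a difference of +8.3. The shift is 2/12 = 16.7 points. This is an upper limit, reached only if no other event keeps the subject in that row.

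**Step 4: Part 2, Day 17.** SAP Section 6, Table 4 lists three Part 2 treatments and separates rifampin once from rifampin QD. The AE windows stop at Day 8 and put everything later under one label. An AE that starts or worsens after the Day 17 co-dose therefore has no rule placing it in the QD column.

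**The case against.** The strongest reply is that the misplacement is not written in the SAP. It needs *occurring* to mean onset and each AE to be one record carrying its highest grade, and neither is stated. The SAP was prepared after review of the eCRF, which is not among the documents and may require a new entry when grade changes; under reading C the problem disappears. The TEAE definition itself depends on knowing when severity rose, the same-term rule expects repeated records of one preferred term, and protocol Appendix 1 judges causality on occurrence or worsening. This stands far enough to rule out saying that the SAP prescribes the error. It does not close the gap, because the tables would then depend on an unwritten convention.

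Four stronger inferences should also be resisted.
- *The TEAE definition is the fault.* An AE that starts on Day 5 is already a TEAE. The open question is which column it enters, which is a matter for the assignment rules.
- *Every AE ongoing across a boundary is affected.* It must also increase in grade after the later dose.
- *The 16.7-point shift applies to each preferred term and grade.* Section 8.6.1 lists no table crossing preferred term with grade.
- *The safety conclusion as a whole is at risk.* Laboratory tests, vital signs and ECGs are also assessed, with baseline reset before LOXO-305 dosing (SAP 8.1.3). All AEs are listed with onset and duration, and no safety inference is planned (SAP 8.6.6). With 12 subjects per part, a careful reader could find the event in the listings.

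**Conclusion.** The concern holds as a gap in the treatment-assignment rule. SAP 8.6.1 has no provision for an AE that begins under one treatment and increases in grade after a later one starts. On the natural reading, such an AE can be shown at its worst grade under LOXO-305 alone or itraconazole alone and be missing from the co-administration column. Given the fixed sequence, that reading can only make the combination look safer.

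For each AE that both spans a boundary and worsens, 8.3 points are missing from the co-administration column, and up to 16.7 points of difference can shift in one grade row of the severity table. This rests on reading A and on 12 subjects per column; fewer subjects receiving the co-dose would make the figures somewhat larger. How many AEs would be affected cannot be judged from the documents, and it may be none. No PK result is touched. The point is worth correcting before database lock, but it does not threaten the trial's primary conclusions.

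**What to change.** Amend the assignment rule in SAP 8.6.1 as follows.
- Count an AE under a treatment if it starts, or increases in CTCAE grade, at or after the first dose of that treatment and before the next treatment starts. Use the grade reached on that treatment.
- Let the earlier treatment keep only the grade reached while on it.
- Apply this at Part 1 Days 8 and 12 and Part 2 Days 8 and 17, so that the Part 2 AE windows match Table 4.
- State that a grade increase is captured as a new dated AE record, and put the same instruction in the eCRF completion guidance.

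The cost is one SAP paragraph and one line of eCRF guidance before database lock, with no extra subjects or visits. If events have already been entered as single records, the date of any grade increase would need to be queried. The one drawback is that a worsening AE can appear under two treatments; a table footnote should say so.

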4.2. Part 2 – Rifampin (CYP3A4 Inducer)

In Part 2, Period 1, a single oral dose of 200 mg LOXO-305 will be administered on Day 1, following a fast of at least 10 hours prior to and 4 hours after dosing with LOXO-305. Blood samples for PK analysis of LOXO-305 in the absence of rifampin will be taken up to 168 hours postdose of LOXO-305 on Day 1.

In Part 2, Period 2, multiple oral doses of 600 mg rifampin will be administered QD from Day 8 until Day 23 inclusive (for a total of 16 consecutive days) and co-administered with a single oral dose of 200 mg LOXO-305 on Days 8 and 17. On Days 8 and 17, a single oral dose of 200 mg LOXO-305 and a single oral dose of 600 mg rifampin will be co-administered in the morning following a fast of at least 10 hours prior to and 4 hours after

dosing with LOXO-305 and rifampin. On Days 9 to 16 and Days 18 to 23, the dose of rifampin will be administered alone at the actual time of the Day 1 LOXO-305 dose (\pm 1 hour), following a fast of at least 8 hours prior to and 2 hours after dosing with rifampin. Blood samples for PK analysis of LOXO-305 in the presence of rifampin will be taken up to 24 hours postdose of LOXO-305 on Day 8 and up to 168 hours postdose of LOXO-305 on Day 17.

Urine samples will be collected on Days 8, 11, 15, and 17 of Part 2 only (and stored for future potential assessment of 6β -hydroxycortisol and free cortisol concentrations to evaluate the level of CYP3A enzyme induction and/or for further exploratory analysis).

There will be a washout period of 7 days between the dose of LOXO-305 on Day 1 (Period 1) and the first dose of rifampin and dose of LOXO-305 on Day 8 (Period 2).

To assess their eligibility to enter the study, potential subjects will be screened within 28 days (Days -29 to -2) and be admitted to the CRU on Day -1 (Check-in). Replacement subjects may be enrolled only if deemed necessary by the Sponsor.

Subjects will be confined at the CRU from the time of Check-in (Day -1) until EOT on Day 24 upon completion of all PK and safety assessments or ET if the subject discontinues. A follow-up phone call will occur for all subjects who received at least 1 dose of study drug (including subjects who are terminated early) 7 days (± 2 days) after EOT or ET.

Replacement subjects may be enrolled only if deemed necessary by the Sponsor.

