6. STUDY TREATMENTS

The study treatment sequence names and ordering to be used in the TFLs are presented in Table 1.

Table 1:	Presentation of Stud	y Treatment Seq	uences in TFLs
----------	----------------------	-----------------	----------------

Part	Study Treatment Sequence	Order in TFLs
1	LOXO-305 alone/LOXO-305 and itraconazole	1
2	LOXO-305 alone/LOXO-305 and rifampin once /LOXO-305 and rifampin QD	2

The study treatment names, and ordering to be used in the TFLs are presented in Table 2,

Table 3. Presentation of Study Treatments in TFLs – Part 1 Non AE and PK Outputs

Study Treatment	Order in TFLs
200 mg LOXO-305 Alone	1
200 mg LOXO-305 + 200 mg itraconazole QD	2

Table 4 and Table 4.

Table 2: Presentation of Study Treatments in TFLs – Part 1 AE Outputs

Study Treatment	Order in TFLs
200 mg LOXO-305 Alone	1
200 mg itraconazole Alone	2
200 mg LOXO-305 + 200 mg itraconazole QD	3

Table 3.Presentation of Study Treatments in TFLs – Part 1 Non AE and PKOutputs

Study Treatment	Order in TFLs
200 mg LOXO-305 Alone	1
200 mg LOXO-305 + 200 mg itraconazole QD	2

Table 4:Presentation of Study Treatments in TFLs – Part 2

Study Treatment	Order in TFLs
200 mg LOXO-305 Alone	1
200 mg LOXO-305 + 600 mg rifampin once	2
200 mg LOXO-305 + 600 mg rifampin QD	3

All treatments described above are the planned treatments. The TFLs will reflect the actual treatments received.

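### The Part 2 TEAE rule in SAP 8.6.1 has no cut at the Day 17 co-dose and so contradicts Table 4, which lists two separate rifampin conditions

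*SAP*

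**What the plan says.** **Part 2 assignment rule (SAP 8.6.1).** TEAEs from Day 1 dosing until Day 8 dosing go to LOXO-305. After that there is one rule: "A TEAE occurring during or after Day 8 dosing will be assigned to 200 mg LOXO-305 and/or 600 mg rifampin". It has no upper limit, and the SAP gives no other rule for assigning Part 2 TEAEs to treatment.

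**Part 2 presentation (SAP 6, Table 4).** The table applies to Part 2 TFLs in general, with no separate AE version. It has three rows: LOXO-305 alone, "200 mg LOXO-305 + 600 mg rifampin once", and LOXO-305 with rifampin QD.

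**Part 1, for contrast.** Part 1 has an AE-specific Table 2 with three rows, including "200 mg itraconazole Alone". Its rule has three matching windows, one of which reads "A TEAE occurring during or after Day 8 dosing and prior to Day 12 dosing will be assigned to 200 mg itraconazole".

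**Dosing inside the open window (SAP 4.2).** LOXO-305 is co-dosed with rifampin on Days 8 and 17. For the other days: "On Days 9 to 16 and Days 18 to 23, the dose of rifampin will be administered alone".

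**Counting (SAP 8.6.1).** The main summaries are introduced by "The frequency of subjects with TEAEs and the number of TEAEs will be summarized for the following categories", and each is by treatment. The rule for a subject with repeated events is: "multiple TEAEs with the same preferred term for the same treatment, this will be counted as 1 TEAE for that treatment", at the highest recorded severity. Subject frequencies are also broken down by "System organ class, preferred term, day of onset, and treatment".

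**Objective (SAP 2.2).** The Part 2 secondary objective covers safety of LOXO-305 alone and with both single and multiple doses of rifampin.

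**The concern.** The design keeps the Day 8 and Day 17 co-doses apart almost everywhere else. Protocol 3.3 gives them different purposes: an acute rifampin dose to inhibit P-gp, and chronic dosing to induce CYP3A and P-gp. The PK comparisons in SAP 8.5.3.1 are separate, and SAP 8.1.3 sets separate Day 8 and Day 17 baselines. The TEAE rule merges them.

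A programmer with only the SAP text cannot follow both 8.6.1 and Table 4. If 8.6.1 prevails, the by-treatment TEAE summaries show one rifampin figure where the objective names two conditions. If Table 4 prevails, someone must invent the assignment rule, perhaps after seeing the data. The rule also leaves events on the rifampin-alone Days 9 to 16 without a stated place in Table 4.

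**Working it through.** **Inputs.** Day 1, 8 and 17 LOXO-305 doses, rifampin on Days 8 to 23, and EOT on Day 24 (SAP 4.2); windows and counting rule (SAP 8.6.1); Tables 2 and 4 (SAP 6). Window lengths are elapsed days to EOT for a subject who completes.

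**Step 1. The plan's own figure.** Rifampin days: 23 − 8 + 1 = 16. This agrees with the 16 consecutive days stated in SAP 4.2.

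**Step 2. Windows against columns.**

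| Part | Assignment windows in 8.6.1 | Treatments listed for AE outputs |
|---|---|---|
| 1 | 3 | 3 (Table 2) |
| 2 | 2 | 3 (Table 4, no AE version) |

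Part 1 matches; Part 2 does not.

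**Step 3. What the open Part 2 window holds.**
- Length: 24 − 8 = 16 days (17 calendar days if both ends are counted).
- LOXO-305 doses: Days 8 and 17, so 2.
- Rifampin doses: 16. Those given alone: 8 (Days 9 to 16) + 6 (Days 18 to 23) = 14.
- Comparator, LOXO-305 alone: 8 − 1 = 7 days and 1 dose.

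**Step 4. The same span with a cut at Day 17 dosing.**

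| Window | Days to EOT | LOXO-305 doses | Rifampin doses |
|---|---|---|---|
| Day 1 to before Day 8 dosing | 8 − 1 = 7 | 1 | 0 |
| Day 8 to before Day 17 dosing | 17 − 8 = 9 | 1 | 9 (Days 8 to 16) |
| Day 17 dosing onward | 24 − 17 = 7 | 1 | 7 (Days 17 to 23) |

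Check: 9 + 7 = 16 days and 9 + 7 = 16 rifampin doses. There are now three windows for three columns. In the middle window 8 of the 9 rifampin doses are given alone, so the cut separates the two co-doses but does not isolate a single rifampin dose.

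**Step 5. Effect on counting.** Take one subject with the same preferred term after the Day 8 co-dose and again after the Day 17 co-dose. Under 8.6.1 as written, this is 1 TEAE in a single rifampin column, at the higher of the two grades. With the cut, it is 1 in each of two columns, each at its own grade. The subject frequencies by system organ class and preferred term change in the same way: the subject appears in one rifampin column now, and in two after the cut.

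**The case against.** **The outcome is undetermined, not known to be pooled.** A reader might infer that every Part 2 TEAE table will show one merged rifampin group. The documents do not support that. Table 4 calls for three columns, and SAP section 1 makes the TFL shells part of the reporting template; those shells were not available and may already hold a split. What stands is that the SAP text contradicts itself and that its only assignment rule pools.

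**Part 1 is not a perfect model.** A reader might infer that Part 1 separates all inhibitor-only days. It does not: the itraconazole-alone window covers Days 8 to 11 only, and events on Days 13 to 18, also itraconazole alone, go to the combination. Moreover, LOXO-305 is co-dosed on Day 8 in Part 2 but not in Part 1, so no clean rifampin-alone window exists before Day 17. A pooled and/or group could therefore be deliberate. If so, the SAP should say so and give Part 2 an AE table that agrees with it.

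**The safety objective is not abandoned.** Vital signs and ECG are summarized by treatment and timepoint (SAP 8.6.3 and 8.6.4), using the separate Day 8 and Day 17 baselines. Protocol 8.4 does not itself require AE tables by rifampin condition. All AEs are listed. The day-of-onset summaries also help if day means study day, which is the natural reading, since 8.6.1 uses onset time for time since last dose; the SAP does not define it. These points limit the harm but do not reconcile the two passages.

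**A cut does not yield a pure single-dose column.** This is correct, and it is why the middle column needs an honest label.

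**Conclusion.** The concern holds as an internal contradiction in the SAP: two Part 2 assignment windows against three listed treatments, with the only stated rule merging two conditions that Table 4 and the secondary objective name separately. Applied literally, that rule sets a group of 16 days, 2 LOXO-305 doses and 16 rifampin doses beside one of 7 days and 1 dose.

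The consequence is confined to descriptive by-treatment TEAE summaries in 12 subjects. Primary PK is unaffected, no inferential safety analysis is planned, and the AE listing allows any reader to separate the events by hand. The day counts assume completers and stop at EOT. Subjects who terminate early contribute less, and because the last window has no end, events reported up to the follow-up call also fall in it. The conclusion concerns the SAP text only; a split in the TFL shells would reduce it to a wording correction.

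**What to change.** Before database lock:

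1. In SAP 8.6.1, cut the Part 2 rule at Day 17 dosing, giving three windows: Day 1 dosing to before Day 8 dosing; Day 8 dosing to before Day 17 dosing; Day 17 dosing onward.
2. Add an AE-output version of Table 4, as Table 2 does for Part 1, with three matching columns. Label or footnote the middle column to show that it includes the rifampin-alone Days 9 to 16 and is not a pure single-dose rifampin window.
3. Align the TFL shells. If they already hold a split, state the same split in 8.6.1.

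A separate sub-column for Days 9 to 16 is optional and not needed to resolve the contradiction.

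**Cost.** A change of SAP wording, one added table and edits to the Part 2 AE shells, with no new data. The downsides are smaller counts per column among 12 subjects and windows of unequal length (7, 9 and 7 days to EOT for completers), which readers must bear in mind when comparing columns.

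### In SAP 8.6.1 the number of TEAEs counts each preferred term once per subject and treatment, so repeat episodes drop out of the event and severity counts.

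*SAP*

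**What the plan says.** SAP 8.6.1 separates two quantities at the start of its summary plan: "The frequency of subjects with TEAEs and the number of TEAEs will be summarized for the following categories". The categories are TEAEs overall, serious and leading to discontinuation, then by severity, and the same again for treatment-related TEAEs.

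The data rules at the end of the section include one that governs summary statistics in general: "If a subject experienced multiple TEAEs with the same preferred term for the same treatment", then "this will be counted as 1 TEAE for that treatment under the maximum severity recorded". It does not distinguish subject counts from event counts.

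What counts as the same treatment depends on the assignment rules in the same section:

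- Both parts, LOXO-305 alone: "A TEAE occurring during or after Day 1 dosing and prior to Day 8 dosing will be assigned to 200 mg LOXO-305".
- Part 1, itraconazole alone: "A TEAE occurring during or after Day 8 dosing and prior to Day 12 dosing will be assigned to 200 mg itraconazole".
- Part 1, combination: "A TEAE occurring during or after Day 12 dosing will be assigned to 200 mg LOXO-305 and/or 200 mg itraconazole".
- Part 2, everything later: "A TEAE occurring during or after Day 8 dosing will be assigned to 200 mg LOXO-305 and/or 600 mg rifampin".

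SAP Table 4, which sets the Part 2 treatment labels for the outputs, instead has separate rows for LOXO-305 with a single rifampin dose and LOXO-305 with daily rifampin. Part 1 has its own AE version of the label table (Table 2). Part 2 has none.

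**The concern.** An event count is worth reporting beside a subject count only if it adds the repeats. Under the last rule it cannot do so within a preferred term, because a subject contributes at most one event per preferred term and treatment. The column would be labelled as a number of events and would hold something else. In the severity tables only the worst episode survives, so a subject with one Grade 2 and two Grade 1 episodes of the same term contributes nothing to Grade 1.

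Tolerability of LOXO-305 with itraconazole, and with single and repeated rifampin, is a secondary objective. The SAP and its output shells are stated to be the template for the study report, so the mislabelled column would carry through. The loss also grows with the length of the window in which repeats can occur, and the windows are not equal, so the shortfall can differ between the treatments being compared.

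**Working it through.** **1. Windows.** The SAP gives rifampin dosing as "Day 8 until Day 23 inclusive (for a total of 16 consecutive days", and 23 − 8 + 1 = 16 reproduces that figure. Elapsed days from the assignment rules and EOT days (Day 19 in Part 1, Day 24 in Part 2):

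- LOXO-305 alone, both parts: 8 − 1 = 7
- Itraconazole alone: 12 − 8 = 4
- LOXO-305 with itraconazole: 19 − 12 = 7
- Part 2 from Day 8, pooled as in 8.6.1: 24 − 8 = 16
- Part 2 split by Table 4: 17 − 8 = 9 and 24 − 17 = 7. Placing the boundary at Day 17 dosing is my assumption, because Table 4 does not assign the days between.

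The follow-up call 7 (± 2) days after EOT or ET is left out. Only related AEs and SAEs are collected then, and it extends the last window of either part.

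**2. What the rule does to one subject (hypothetical).** Suppose headache is recorded at Grade 1 on Day 8, Grade 2 on Day 12 and Grade 1 on Day 18 in Part 2, each after dosing.

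- Recorded: 3 TEAEs, two at Grade 1 and one at Grade 2.
- Pooled label: 1 TEAE, at Grade 2.
- Table 4 labels: the Day 8 and Day 12 episodes become 1 at Grade 2 and the Day 18 episode counts 1 at Grade 1, so 2 in all.

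The collapse occurs under either labelling. Only its extent changes.

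**3. Size under an assumed rate.** The documents give no recurrence rate. Assume that one preferred term recurs in a subject as a Poisson process at rate r per day, equal in all windows, with r from 0.01 to 0.20. Over T days:

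- expected recorded events = rT
- expected count under the rule = 1 − exp(−rT)
- share lost = 1 − [1 − exp(−rT)]/(rT)

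For r = 0.05 and T = 16, rT = 0.8, 1 − exp(−0.8) = 0.551, and the loss is 1 − 0.551/0.8 = 31.2%. For T = 7, rT = 0.35, and the loss is 1 − 0.295/0.35 = 15.6%.

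| Window | T (days) | r = 0.01 | r = 0.05 | r = 0.20 |
|---|---|---|---|---|
| Itraconazole alone | 4 | 2.0% | 9.4% | 31.2% |
| LOXO-305 alone; LOXO-305 + itraconazole | 7 | 3.4% | 15.6% | 46.2% |
| Part 2 pooled from Day 8 | 16 | 7.6% | 31.2% | 70.0% |
| Part 2 rifampin once (Table 4) | 9 | 4.4% | 19.5% | 53.6% |
| Part 2 rifampin QD (Table 4) | 7 | 3.4% | 15.6% | 46.2% |

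If subjects differ in their rates (gamma frailty, shape 1), the loss is rT/(1 + rT). At r = 0.05 this is 0.35/1.35 = 25.9% for 7 days and 0.8/1.8 = 44.4% for 16 days. Simulation gave 26.0% and 44.4%.

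**4. In counts, for 12 Part 2 subjects at r = 0.05.** LOXO-305 alone: 12 × 0.35 = 4.2 recorded against 12 × 0.295 = 3.5 counted. Pooled rifampin: 12 × 0.8 = 9.6 against 12 × 0.551 = 6.6. The ratio falls from 16/7 = 2.29 to 1.86.

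**5. When the order would change.** The loss rises with rT. The pooled rifampin window therefore loses more than LOXO-305 alone unless its daily rate is below 7/16 = 0.44 of the LOXO-305 alone rate.

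**The case against.** The other side has a good deal to say.

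- **Recurrence is not hidden altogether.** A reader might infer that the rule erases a repeat after the second LOXO-305 dose. The documents do not support that. SAP 8.6.1 also plans frequency-of-subjects tables by day of onset, where an event on two days can appear under both, and every AE is listed with onset time and duration. With 12 subjects in Part 2 the listings can be read directly. This stands. It does not make the event column correct.
- **The Part 2 emphasis is conditional.** A reader might infer that an event after Day 8 and again after Day 17 must count as 1. That follows from the pooled assignment in 8.6.1. Under Table 4 the two fall in different treatments and count as 2, and the Part 2 losses come close to those of the other windows. This stands.
- **Extreme examples are not evidence.** A daily recurring event counted once instead of up to 16 times is arithmetically possible. It needs a separate AE record of the same term after every rifampin dose, and nothing in the documents suggests that.
- **Raw counts depend more on window length.** At equal daily rates they differ 2.29-fold purely through duration, against 1.86 at r = 0.05 under the rule. This is a reason to read raw counts beside the window lengths. It is no reason to label pairs as events.
- **The rule is pre-specified and keeps the worst grade, and the output shells may define the column.** The shells are not among the documents, so they may resolve the label. The SAP text itself makes no exception.

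**Conclusion.** The point holds as a mismatch between label and content. Followed literally, the number of TEAEs is the number of distinct subject-by-preferred-term pairs per treatment, and repeat episodes, including lower-grade ones in the severity tables, are missing from the event counts. The collapse is within a subject; events in different subjects are not merged.

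The size cannot be derived from the documents. The percentages above rest on assumed rates, equal across windows, and show direction and sensitivity only. On that basis the understatement is clearly larger in Part 2 only if the pooled Day 8 onward label is used.

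The weight is modest. Subject frequencies, maximum severity and listings are intact, no safety inference is planned, and the primary PK analysis is not touched.

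**What to change.** In SAP 8.6.1, limit the once-per-preferred-term, maximum-severity rule to the frequency-of-subjects summaries. In the number-of-TEAEs summaries, overall, by severity and by relationship, count every recorded TEAE at its own severity. If the sponsor prefers the collapsed count, keep it and label the column as subject-by-preferred-term counts.

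Separately, reconcile the Part 2 AE assignment in 8.6.1 with Table 4, either by splitting the assignment to match the two rifampin treatments or by adding an AE version of the label table as Part 1 has. State where TEAEs between Day 8 and Day 17 dosing fall.

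The cost is one or two sentences and a small programming change, with nothing altered in conduct or data collection. Event counts may be slightly higher. Because raw counts grow with follow-up time, the tables should carry a footnote giving the window length for each treatment.
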